Study Title: Single Breath Hold MRI

NCT02434471

IRB Review Date: 04/16/2015

1) Protocol Title: Single Breath Hold Abdominal MRI

Short Title: Single BH Abdominal MRI

2) Purpose of the Study: To develop a single breath hold abdominal MRI protocol, and compare the image quality of respiratory triggered 3D T₁-weighted images against conventional breath hold images.

3) Background and Significance: T₁-weighted imaging is a mainstay of abdominal MRI, providing information about both intrinsic tissue properties and lesional vascular properties (when an intravenous contrast agent is administered).

However, T₁-weighted imaging is highly motion-sensitive and typically performed in a breath hold. Particularly in ill patients, such as inpatients and those presenting to the Emergency Department, breath holding capacity may be diminished, and high-quality T₁-weighted imaging may be difficult to obtain. Many motion compensation methods have been developed, including respiratory triggered and radial imaging. However, these methods are, in general, too time-consuming for routine use in dynamic liver MRI, which requires the acquisition of arterial, portal venous, and equilibrium phase images in relatively rapid succession.

Recently, high temporal acceleration factors for T₁-weighted imaging have been combined with respiratory triggering in order to produce respiratory triggered sequences that are more suitable for dynamic imaging; these are based on combining conventional respiratory triggering with optimized versions of the conventional LAVA (Liver Acquisition with Volume Acquisition) pulse sequence. Such a sequence is rapid enough for portal venous and equilibrium phase imaging during free breathing, though not necessarily for arterial phase imaging. This sequence could allow for an optimized liver MRI protocol that could be performed with only one breath hold in the arterial phase, and no additional breath holds, in contrast to the typical examination which typically requires four or more breath holds.

The purpose of this study is to evaluate a single breath hold abdominal MRI protocol, to and compare the image quality of respiratory triggered 3D T₁-weighted images against conventional breath hold images.

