4) Design and Procedures: This will be a prospective study with written informed consent obtained. Patients presenting to DUHS for clinical abdominal MRI at the Duke Medical Pavilion (inpatients and emergency department patients) as part of their routine care will be included. In addition to their typical contrast-enhanced abdominal MRI protocol, we will acquire three extra image sets:

- 1) Respiratory-triggered T₁w DISCO LAVA precontrast
- 2) Respiratory-triggered T₁w DISCO LAVA in the portal venous phase

3) Respiratory-triggered T_1 w DISCO LAVA in the equilibrium phase

The only modification to the patients' clinical scan protocol will be to add these three image sets. This is expected to add about 5 minutes to their scan time, and will not significantly affect clinical workflow/throughput. All patients presenting for imaging on the appropriate MRI scanner while a CRC is available to obtain written informed consent, who are able to give consent, will be offered the opportunity to participate in this study. The clinical image data which are routinely sent to PACS will be deidentified and exported for offline analysis, and raw data may be collected in some cases for reprocessing.

Only subjects presenting for clinical MRI will be included. Up to 100 subjects will be included. On data collection, an investigator will assign a serial code number and document pertinent demographic information such as patient age and gender. The code number assigned will not be derived from any personal identifier for the subject. The investigator will also access Maestro records to confirm the indication for the examination and to obtain laboratory values near the time of the examination. The imaging examinations and clinical information will have all patient identifiers removed, including the name, medical record number, and date of birth.

Subsequently, the individual MRI examinations and clinical information will be labeled with a unique assigned code number. After all relevant information is recorded and the exams/reports coded, the investigator will destroy the key linking any subject's personal history information to the assigned code numbers.

Rationale for prospective design: This project would not be possible to perform in a retrospective setting, because clinical rationale for performing the additional T_1 -weighted acquisitions above is lacking.

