11) Costs to the Subject: There will be no costs to any subjects.

12) Data Analysis and Statistical Considerations: Up to 100 subjects will be included in the study population.

Two investigators will independently evaluate MRI examinations. They will assign motion scores and other measures of image quality between respiratory triggered and corresponding breath hold acquisitions. Comparisons between motion scores as well as other image quality scores will be made using the Wilcoxon rank sum test. Inter-reader agreement will be assessed using the Interclass Correlation Coefficient.

The motion scoring scale has been used in prior studies and is described as follows: 1 = no motion artifact; 2 = minimal motion artifact, no effect on diagnostic quality; 3 = moderate motion artifact with some, but not severe, effect on diagnostic quality; 4 = severe motion artifact, images degraded but interpretable; and 5 = extensive motion artifact, images nondiagnostic.

13) Data and Safety Monitoring: An investigator will assign a serial code number and document pertinent clinical information. The code number assigned will not be derived from any personal identifier for the subject. The imaging exams and clinical data will have all patient identifiers removed, including the name, medical record number, and date of birth.

Subsequently, the imaging exams and clinical data will be labeled with a unique assigned code number. After all relevant information is recorded and the exams/data coded, the study coordinator will destroy the key linking any subject's personal history information to the assigned code number. Available coded clinical data will be reviewed following the completion of imaging exam evaluation. All data will be retained in a password-protected folder on a

research shared drive supported by DHTS. A formal data safety and monitoring board will not be used.

14) Privacy, Data Storage & Confidentiality: Every effort will be made to ensure subjects' confidentiality. All study files containing subject information will be kept on secure password protected computers with only study staff having access to the files. No identifying patient information will be included on any images or reported in any subsequent publications. Study data will be kept only for a period of six years after the study is completed, at which time all relevant study documents will be destroyed.

No identifiable PHI will be released outside of DUHS.

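### Section 12 compares motion and unnamed other quality scores over three phases and two readers with no primary comparison, significance level, reader rule or error control, so a headline claim could rest on a selected result

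*Combined protocol and SAP*

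**What the plan says.** The purpose in Section 2 is to "compare the image quality of respiratory triggered 3D T₁-weighted images against conventional breath hold images". No phase, measure or direction is singled out.

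Section 4 adds the respiratory-triggered (RT) series to the routine scan: "we will acquire three extra image sets". These are precontrast, portal venous and equilibrium, so there are three phases in which RT can be set against breath hold (BH).

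Section 12 supplies the whole analysis:
- Sample: "Up to 100 subjects will be included in the study population".
- Readers: "Two investigators will independently evaluate MRI examinations".
- Scores: "They will assign motion scores and other measures of image quality between respiratory triggered and corresponding breath hold acquisitions".
- Test: "Comparisons between motion scores as well as other image quality scores will be made using the Wilcoxon rank sum test".
- Readers' agreement: "Inter-reader agreement will be assessed using the Interclass Correlation Coefficient".

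Motion has a five-point scale defined level by level. The other measures have neither names nor scales. Neither Section 12 nor any other section states a primary comparison, a significance level, a multiplicity rule, or how two readers' scores become one comparison.

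**The concern.** RT could score better on motion in one phase and worse in another, or differ between readers, or do well on motion and badly on another measure. The plan has no rule for which of these results answers the study question. Because the other measures are not listed, their number and choice can also be settled after scores have been seen.

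A statement that RT is better or worse than BH could then rest on whichever phase, reader or measure crossed a threshold that is itself unstated. The error rate of such a statement is not fixed by the plan, and a reader of the results could not tell a planned finding from a selected one.

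**Working it through.** **No figure to reproduce.** The documents give no significance level, power, effect size or error rate.

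**Inputs**
- Phases: 3 (Section 4).
- Readers: 2 (Section 12). Whether tests are run per reader or on combined scores is not stated, so both are shown.
- Measures: motion plus others. The plural implies at least two others, so at least three in total; the exact number is not given.
- Level: 5% two-sided per test (assumed).
- Patients: 100, the stated ceiling.

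**Upper benchmark: independent tests.** The chance of at least one p < 0.05 when nothing differs is 1 − 0.95^m, where m = phases × reader comparisons × measures.

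| Tests counted | m | 1 − 0.95^m |
|---|---|---|
| Motion, readers combined | 3 × 1 × 1 = 3 | 14.3% |
| Motion, per reader | 3 × 2 × 1 = 6 | 26.5% |
| Three measures, readers combined | 3 × 1 × 3 = 9 | 37.0% |
| Three measures, per reader | 3 × 2 × 3 = 18 | 60.3% |

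The figure passes 50% only at m = 14 (51.2%; m = 13 gives 48.7%).

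**Allowing for correlation.** Scores from the same patients are not independent. In simulations with no true difference, n = 100, assumed category shares of 30/35/20/10/5% and 1,500 runs per setting, testing per reader and phase gave:

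| Share of variance common to a patient's RT and BH scores | Measures | Rank sum (planned) | Signed-rank (paired) |
|---|---|---|---|
| 0 | 1 | 25% | 25% |
| 30% | 1 | 11% | 22% |
| 50% | 1 | 5.5% | 24% |
| 0 | 3 | 50% | 49% |
| 30% | 3 | 26% | 48% |
| 50% | 3 | 11.5% | 44% |

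Simulation standard error is at most √(0.5 × 0.5/1500) = 1.3 points.

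With a shared patient effect, the rank sum test ignores the pairing and rejects too rarely: its per-test error falls to about 1–2% instead of 5%.

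A further set of simulations at n = 100, which also averaged the two readers, gave these ranges:
- Motion alone, rank sum: about 1–7% with readers averaged, 5–13% per reader.
- Motion alone, paired test: about 13–22%.
- Three measures: about 9–33% with rank sum, 34–53% with a paired test.

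**After naming one primary comparison.** Its error rate is 5% by construction. Keeping every test with a Bonferroni correction would instead need 0.05/6 = 0.0083 per test for motion alone per reader, or 0.05/18 = 0.0028 for three measures.

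**The case against.** A reader might infer that at least one significant result is likely by chance, or that the error rate is far above 5%. The documents do not support either statement. More than 50% needs at least 14 independent tests, that is, three or more measures tested separately by phase and reader. The plan never says that tests are run per reader or even per phase, and gives no count of measures. For motion, the only measure defined, the planned test can have a chance of error near or below 5% when readers are averaged and patients' two scores are correlated.

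A reader might also infer that all scores have equal standing. Motion is listed first and is the only one with a scale, so it has some prominence, though it is nowhere called primary.

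Nor does the plan say that any single significant test decides the study. The goal of one arterial-phase breath hold and no others suggests that RT should be adequate in all three phases, and requiring every phase to succeed does not inflate error. Finally, this is a single-site developmental imaging study with no confirmatory claim, so strict familywise control is partly a matter of preference.

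These points limit the size of the concern. They do not supply the missing rule: the all-phases reading is as unstated as the any-test reading. The low rank sum figures are not a designed safeguard either. They arise from applying an unpaired test to paired scores, and correcting that restores the inflation.

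**Conclusion.** The concern holds as a gap in prespecification with moderate error inflation. There is no primary comparison, level, reader rule, list of measures or error control, so selective emphasis cannot be excluded.

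For motion alone, the chance of a false positive is at most about 14% (readers combined) or 26% (per reader). It is about 1–13% under the planned test when the two techniques share a patient effect; without one it approaches the independence figure. With three measures it is about 9–33% under the planned test and 34–53% under a paired test.

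These sizes rest on an assumed 5% level, an assumed number of measures and assumed correlations and category shares. The omissions themselves rest on the text alone.

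**What to change.** Before scoring begins, amend Section 12 to:

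1. Name one primary comparison: the motion score averaged over both readers, RT versus BH, in one stated free-breathing target phase. Portal venous is an example. The sponsor should confirm the choice, because Section 3 names portal venous and equilibrium together and does not rank them.
2. Test it with a paired test, such as the Wilcoxon signed-rank test, at two-sided 5%.
3. Test motion in the remaining two phases in a stated fixed order, each at 5% and only if the previous step succeeds.
4. List the other quality measures and their scales in advance, and report them with estimates and confidence intervals as exploratory.

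The cost is protocol wording, with no added scans or patients. The downside is that the secondary measures, and later phases if an earlier step fails, cannot support a significance claim on their own.

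### Section 12 names an unpaired test (Wilcoxon rank sum) for image scores that are paired within patient; if those scores are positively correlated, the test is conservative and loses power

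*Combined protocol and SAP*

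**What the plan says.** Section 4 (Design and Procedures) describes one group of patients, each imaged both ways: "In addition to their typical contrast-enhanced abdominal MRI protocol, we will acquire three extra image sets". The additions are respiratory-triggered acquisitions precontrast, in the portal venous phase and in the equilibrium phase. It adds that "The only modification to the patients' clinical scan protocol will be to add these three image sets", so the patient's own breath hold images are kept as the comparator. There is no separate control group.

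Section 12 (Data Analysis and Statistical Considerations) states the comparison: "They will assign motion scores and other measures of image quality between respiratory triggered and corresponding breath hold acquisitions". Two readers score independently, motion is graded on an ordinal scale from 1 to 5, and on size the section says only "Up to 100 subjects will be included in the study population". The one comparative test is named in this sentence: "Comparisons between motion scores as well as other image quality scores will be made using the Wilcoxon rank sum test".

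The document mentions no signed-rank test, paired analysis or other allowance for within-patient dependence. It also does not say how two readers and three phases enter the test, and it gives no significance level, effect size, power or expected correlation.

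**The concern.** The rank sum test takes its variance from two independent samples. When both scores come from the same patient, that variance is wrong unless the two scores are uncorrelated.

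- **Positive correlation.** This is plausible, because a patient who moves a lot may score badly with both techniques. The test then rejects too rarely and gives up the main statistical benefit of imaging each patient both ways. A real difference, in either direction, can be missed, and the miss could be taken for equal image quality.
- **Negative correlation.** This is possible if triggering helps mainly those who hold their breath poorly. The test then rejects too often.

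This is the only test named for the study's stated purpose of comparing triggered with breath hold image quality.

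**Working it through.** The document gives no power or error figure to reproduce, so the check asks how the named test behaves on data with this structure.

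**Inputs from the document.** Up to 100 patients; two techniques per patient; three phases; two readers; a 5-point ordinal score; the rank sum test.

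**Assumptions, since the document gives none of these.** Two-sided 5% level; score shares 25/40/20/10/5% for grades 1 to 5; latent shift 0.3 SD (0.32 points on the scale); latent within-patient correlation ρ from -0.2 to 0.7; one score per technique per patient.

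**Step 1: formula (normal approximation, continuous scores).** An unpaired test takes the variance of the difference in means as 2σ²/n. With pairing it is 2σ²(1-ρ)/n. With δ the shift in SD units:

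- True size of the unpaired test = 2[1-Φ(1.96/√(1-ρ))]
- Power, unpaired = Φ[(δ/√(2/n) - 1.96)/√(1-ρ)]
- Power, paired = Φ[δ/√(2(1-ρ)/n) - 1.96]

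Size at ρ = 0.3: 1.96/√0.7 = 2.343, giving 1.9%. At ρ = 0.5: 1.96/√0.5 = 2.772, giving 0.6%. At ρ = 0.7: 1.96/√0.3 = 3.578, giving 0.03%. At ρ = -0.3: 1.96/√1.3 = 1.719, giving 8.6%.

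Power for n = 100, δ = 0.3: δ/√(2/n) = 0.3/0.1414 = 2.121. At ρ = 0.5, unpaired is Φ(0.161/0.707) = 59% and paired is Φ(2.121/0.707 - 1.96) = 85%.

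**Step 2: simulation of 5-point scores.** Pairs were cut from a bivariate normal, with 6,000 replicates per cell (Monte Carlo error about 0.3 points at 5% and 0.65 points at 50%). With 100 patients:

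| Latent ρ | Rank sum type I error | Power, rank sum | Power, signed-rank |
|---|---|---|---|
| -0.2 | 7.0% | 51% | 44% |
| 0 | 5.4% | 50% | 49% |
| 0.3 | 2.1% | 52% | 62% |
| 0.5 | 0.7% | 51% | 75% |
| 0.7 | 0.2% | 52% | 91% |

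Signed-rank type I error stayed at 4.5-5.4% throughout. At ρ = -0.2 the rank sum test's higher power comes from exceeding its level.

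Because 100 is a ceiling, the same was run with 50 patients. Power, rank sum v signed-rank, was 26% v 36%, 24% v 46% and 19% v 63% at ρ = 0.3, 0.5 and 0.7.

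**Step 3: sensitivity to the score distribution.** With shares 25/35/20/15/5%, 10,000 replicates and 100 patients, rank sum type I error was 2.4%, 1.0% and 0.2% at ρ = 0.3, 0.5 and 0.7. Power was 53% v 65%, 51% v 76% and 52% v 91%. The conclusion does not depend on the particular shares.

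**Step 4: readers and phases.** The plan neither states nor rules out pooling the 2 × 3 = 6 scores per technique. If they were pooled as independent, the variance would be off by the factor 1 + 5ρ_w - 6ρ_b, where ρ_w is the correlation within a technique and ρ_b the correlation between techniques.

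- ρ_w = ρ_b = 0.5: 1 + 2.5 - 3 = 0.5, so the test is conservative (simulated size 1.0%).
- ρ_w = 0.6, ρ_b = 0.3: 1 + 3 - 1.8 = 2.2, so the test is liberal (simulated size 17.9%).

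Over eight assumed variance splits, pooled rank sum size ran from 0.6% to 19.7%. Pooling the six differences in a signed-rank test gave 8.1% to 26.4%. Signed-rank for one phase, with one value per patient, gave 4.6-5.9%. Changing the test name alone is therefore not enough; the unit of analysis must be named too.

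**The case against.** The strongest reply has five parts.

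1. **The loss depends on the chosen effect.** This stands in part. With 100 patients and a shift of 0.5 SD, power is 94% v 97% at ρ = 0.3 and 96% v 99% at ρ = 0.5. At shift 0.3 and low correlation the gap is also small: 51% v 53% at ρ = 0.1 and 52% v 59% at ρ = 0.2. With 50 patients the gap remains at 0.5 SD. There δ/√(2/n) = 0.5/0.2 = 2.5, and at ρ = 0.5 the formulas give Φ(0.54/0.707) = 78% against Φ(2.5/0.707 - 1.96) = 94%.
2. **The signed-rank test has its own assumption.** This stands. It holds its level when the differences are symmetric about zero under the null. If 20% of patients improve by 2 points, 40% worsen by 1 and 40% do not change, the mean difference is zero, yet the test rejects in about 14% of replicates with 100 patients. That qualifies the replacement but does not rescue the rank sum test.
3. **The pooling figures are illustrative.** This stands. They describe an analysis that the plan does not specify, and they serve only to show why the unit of analysis must be stated.
4. **A conservative test creates no false positives, and the plan makes no equivalence claim.** Both are true under positive correlation. Reading a null result as equal quality is a risk rather than something the plan says, and a paired test does not remove it. It does reduce the chance of missing a real difference.
5. **The wording may be a slip for signed-rank, correctable at any time before analysis.** It may be. Both techniques sit within one coded examination, so the pairing survives destruction of the linking key. But an analyst following Section 12 as written would run the unpaired test.

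**Conclusion.** The concern holds. The mismatch between a paired design and an unpaired test follows from Sections 4 and 12 alone and needs no assumption.

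Its size does rest on assumptions. For a 0.3 SD shift with 100 patients, the power given up is about 10, 24 and 39 percentage points at latent correlations of 0.3, 0.5 and 0.7 (62-52, 75-51, 91-52). It is nil at zero correlation, and small with 100 patients once the shift reaches 0.5 SD. Under negative correlation the fault changes sign and the type I error rises to 7.0% at ρ = -0.2. Because this is the only comparative test in the plan, it should be corrected before any scores are analysed.

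**What to change.** In Section 12, replace the rank sum test with the Wilcoxon signed-rank test on within-patient differences (respiratory triggered minus breath hold). Run it separately for the precontrast, portal venous and equilibrium phases, with the patient as the unit of analysis. State in advance whether it is done for each reader or on the mean of the two readers; either is acceptable. Say that readers and phases will not be pooled as independent observations. Since many differences on a 5-point scale will be zero, it is also worth saying how zeros are handled.

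The cost is one or two sentences, with no extra patients, scans or readings. If the correlation turns out to be zero, nothing is lost: power is 50% for rank sum and 49% for signed-rank, which is within simulation error.

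### Does naming the 'Interclass' correlation coefficient, with no form stated, undermine the assessment of reader agreement?

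*Combined protocol and SAP*

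**What the plan says.** Section 12 (Data Analysis and Statistical Considerations) of the combined protocol and SAP sets up the reading as follows: "Two investigators will independently evaluate MRI examinations". On what is scored, it says: "They will assign motion scores and other measures of image quality between respiratory triggered and corresponding breath hold acquisitions". Motion is graded on a five-point anchored scale whose upper end reads "4 = severe motion artifact, images degraded but interpretable; and 5 = extensive motion artifact, images nondiagnostic". The only statement on agreement is "Inter-reader agreement will be assessed using the Interclass Correlation Coefficient".

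The documents do not give the model (one-way or two-way), the type (consistency or absolute agreement), the unit (one reader or the mean of two), a confidence interval or a threshold for acceptable agreement. They describe no reader calibration or consensus step. They also attach no consequence to the coefficient: no reading is repeated, excluded or adjudicated because of its value.

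**The concern.** An interclass correlation, in the strict sense, is the ordinary product-moment correlation between two distinct variables. It measures whether the readers rank and space the images alike. If one reader always scores a category higher, it stays at 1.

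Reading the word as intraclass removes only part of the difficulty. One-way and absolute-agreement intraclass coefficients count an offset as disagreement, but the two-way consistency form does not, and the sentence permits any of them. Because each category is tied to a statement about diagnostic quality, a one-category offset is a real difference of opinion. At the top of the scale it separates images that can be read from images that cannot. Readers who seldom gave the same score could therefore be reported as highly reliable, and the form could be chosen after the scores were seen.

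**Working it through.** **Inputs.** From Section 12: two independent readers, a 1 to 5 scale and an upper limit of 100 subjects. The plan states no agreement value, target or precision, so there is no figure of its own to reproduce. Score distributions, reader error and reader offset are assumptions throughout.

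**Formulae**, for k = 2 readers and n images, with mean squares for images (MSR), readers (MSC) and residual (MSE):

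- Consistency: C = (MSR − MSE) / (MSR + (k − 1)·MSE)
- Absolute agreement: A = (MSR − MSE) / (MSR + (k − 1)·MSE + k·(MSC − MSE)/n)

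In population terms, with image variance s², error variance e² and a fixed offset b between the readers, C = s²/(s² + e²) and A = s²/(s² + e² + b²/2).

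**Step 1: the extreme case.** Take n = 100, with reader 1 giving 25 images each of scores 1, 2, 3 and 4, and reader 2 always one higher. Then MSR = 2.525, MSC = 50 and MSE = 0. The Pearson correlation and C are both 1.00. A = 2.525 / (2.525 + 2 × 50/100) = 2.525/3.525 = 0.72. Exact agreement is 0%. With reader 1's scores bunched at the low end (80 images scored 1 and 20 scored 2), A falls to 0.24 while Pearson and C stay at 1.00. The concern is therefore algebraically sound.

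**Step 2: the population formula at graded offsets.**

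| s², e² | Form | b = 0 | b = 0.25 | b = 0.5 | b = 1 |
|---|---|---|---|---|---|
| 1.0, 0.25 | C | 0.80 | 0.80 | 0.80 | 0.80 |
| 1.0, 0.25 | A | 0.80 | 0.78 | 0.73 | 0.57 |
| 0.7, 0.3 | C | 0.70 | 0.70 | 0.70 | 0.70 |
| 0.7, 0.3 | A | 0.70 | 0.68 | 0.62 | 0.47 |

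For example, with s² = 0.7, e² = 0.3 and b = 0.5, A = 0.7/(1.0 + 0.125) = 0.62. The offset enters as b²/2, so small offsets cost little.

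**Step 3: scores rounded and limited to 1–5.** Simulation with 400,000 images per setting; mean severity 1.8, between-image SD 0.8, reader error SD 0.3:

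| Offset (categories) | Pearson | C | A | Exact agreement |
|---|---|---|---|---|
| 0 | 0.77 | 0.77 | 0.77 | 72% |
| 0.25 | 0.77 | 0.77 | 0.74 | 66% |
| 0.5 | 0.76 | 0.76 | 0.66 | 52% |
| 1 | 0.76 | 0.75 | 0.47 | 20% |

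Over eight settings (mean 1.8 or 2.5, SD 0.8 or 1.1, error SD 0.3 or 0.5), C minus A is 0 with no offset, 0.01 to 0.03 at 0.25, 0.05 to 0.10 at 0.5 and 0.17 to 0.30 at 1.

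**Step 4: how often the offset crosses the readable/nondiagnostic line.** In the setting tabulated in step 3, the readers fall on opposite sides of the line between 4 and 5 for about 0.5% of images at an offset of 0.5 and 2.3% at an offset of 1. With mean severity 2.5 the share at an offset of 1 is about 11% to 16%.

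**Step 5: what reaches the main comparison.** If a reader adds b to every score, the triggered score becomes T + b and the breath-hold score H + b. The difference is (T + b) − (H + b) = T − H, and the ordering of that reader's scores is unchanged. On a bounded, rounded scale the cancellation is approximate at the ends. The choice of agreement coefficient does not enter the comparison at all.

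**The case for a change.** The best argument for amending the plan is that every image-quality result rests on two readers' subjective scores, and this sentence is the only check on whether the readers are interchangeable. The stated goal is agreement, not correlation. Correcting the word alone would let the same data be reported as 1.00 or as 0.24 to 0.72 in the pure-shift cases, and fixing the form in advance costs one sentence.

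Much of this stands. The form is not named, the forms can diverge, and naming one would be good practice. But the argument needs two further things: a systematic offset large enough to matter, and a conclusion that depends on the coefficient. The documents point to neither. The scale has worded anchors and is described as used before, so a full-category bias is the unfavourable end of the range. Standard intraclass forms other than consistency already penalise an offset. The mean difference between readers and their exact agreement can be computed from the same scores at any time, so nothing is lost by the plan's silence. Separate coefficients by technique and phase would go beyond anything the wording gap requires.

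**Conclusion.** No change is called for. The word is most likely a clerical slip, and the unstated form is a detail that an analyst would settle and report with the result. The choice makes no difference if the readers share a common level, and little (0.01 to 0.03) at a quarter-category offset. It becomes substantial (0.17 to 0.30) only if one reader scores about a full category above the other. Those sizes rest on assumed score distributions and error, since the documents contain no agreement data. Whatever the offset, the effect is confined to a secondary descriptive coefficient with no decision rule. The coefficient chosen plays no part in the comparison of respiratory-triggered with breath-hold images, nor in the ceiling of 100 subjects. A reader of the eventual report should check which form was used, but the plan itself can stand.
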